## **Secondary objectives:**

# (S1) To demonstrate that worsening of MS-related disability is associated with loss of thalamus volume also if loss of whole brain volume is within the normal range.

Based on the individual results for TVL and BVL derived from three routine MRIs, the study population will be divided into four distinct subgroups as suggested by Opfer et al. (2020) and shown in Figure 4.

**Figure 4.** Clinical characteristics of group 2 ( $\sim$ 25% of all patients) are of particular interest and whether group 2 is statistically distinct with regard to clinical and imaging data.

The probable frequencies for these groups were also taken from this paper:

**Group 1**: normal BVL, normal TVL (estimated frequency ~50% of the total relapsing-remitting MS population); **Group 2**: normal BVL, pathological TVL (~25%); **Group 3**: pathological BVL, pathological TVL (~25%); **Group 4**: normal TVL, pathological BVL (~0%)

We will use the cut-offs for normal and pathological TVL presented in Opfer et al. (2020) and corresponding cut-offs for BVL as published in Opfer et al. (2018a and 2018b).

At month 24 study subjects shall be grouped based on their individual EDSS increase in patients with (confirmed) disability progression and patients without disability progression.

Dichotomization is based on the following cut-offs:

**Group A** (with evidence of disability progression / confirmed disability progression)

- −1.0 increase for study subjects with baseline EDSS scores from 1.0 to 5.0
- −0.5 increase for study subjects with baseline EDSS scores equal or higher than 5.5

**Group B** (no evidence of disability progression)

We will perform a chi-square test to see if there is a significant difference between the frequency of patients with progressive disability (group A) and without evidence of progressive disability (group B).

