# (S2) To demonstrate that the change of thalamus volume during 24 months is predictive of the change of disability during the following 12 months (months 24-36).

We will build a statistical model based on clinical and MRI (estimated from three MRI measurements sampled at baseline (BL), at month 12 and at month 24) parameters to predict disability progression between month 24 and month 36. EDSS will be determined at additional visits at 30 and 36 months. The annual change of EDSS between months 24 and 36 will be determined by linear regression of EDSS versus time including 24, 30 and 36 months. The annual change of EDSS between months 24 and 36 will be dichotomized using the same predefined cutoff as deployed for (S1) (see above). The association between dichotomized disability change between 24 and 36 months and baseline (BL) parameters and TVL between baseline and 24 months will be tested using the chi-square statistic.

The following parameters will be used:

- Clinical scores / characteristics @ BL:
  - Age and sex

\_

<sup>1 Guideline on clinical investigation of medicinal products for the treatment of Multiple Sclerosis from EMA as of 26 March 2015

- disease duration (DD)
- EDSS
- Therapy
- MRI @ BL
  - z-scores of thalamus and whole brain volume
  - T2 lesion load
- MRI @ BL, month 12 and month 24
  - TVL and BVL

The model will be based on multivariate regression or support vector machines. The performance of the model will be characterized using a receiver operating characteristic (ROC) curve. The ROC will be evaluated with respect to accuracy, area under curve (AUC), sensitivity (true positive rate) and specificity (true negative rate). Within each classifier including both clinical and neuroradiological features, permutation importance will be calculated for each feature and for the random variable: only parameters whose importance are higher than the random variable's importance, will be considered as relevant in the classifier.

Baseline volumes for thalamus and whole brain will be estimated using a novel convolutional neural network-based approach, recently submitted for publication (Opfer et al. 2021).

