## Secondary objectives

For addressing the secondary objectives groups 1 and 2 as defined in the statistical analysis methods are particularly relevant, but differences between all groups will be equally looked at. We assume an annual dropout rate of 15%. 24 months after baseline EDSS measurement study subjects shall be grouped based on their individual EDSS progress: group A comprises study subjects with (confirmed) disability progression and group B study subjects without disability progression. We assume that the incidence of study subjects in group 1 who belong to group A (with (confirmed) disability progression) is 5%. We further assume that the incidence of study subjects in group 2 who belong to group A (with (confirmed) disability progression) is 15%. The difference between groups 1 and 2 is significant (accepting a type-I error of 0.05 and a type-II error of 0.20) if the size of group 1 and group 2 is 196 and 98, respectively, 24 months after baseline EDSS measurement. Taking the annual dropout rate of 15% into account approximately 600 study subjects should be included.

The basic figures for incidence rates of disability progression in early MS patients for short and longer clinical trials were derived from Röver et al. (2015).

Similarly, we assume that 5% of patients in groups 2 and 3 (pooled) show disability progression between month 24 and month 36, whereas in group 1 the incidence is approximately zero. The difference between the pooled group and group 1 is significant (assuming a type I error of 0.05 and a type II error of 0.20) when the size of each of group 1 and the pooled group is 152.

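### The S2 prediction model lists ten predictors, but the plan's own S2 rates imply about eight events; any AUC computed on the fitting data would be strongly optimistic

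*Protocol*

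**What the plan says.** Protocol section 4, secondary objective S2, plans a model for disability progression between months 24 and 36, built on clinical and MRI parameters. The listed parameters are age, sex, disease duration, EDSS, therapy, thalamus z-score, whole-brain z-score, T2 lesion load, TVL and BVL. On the method: "The model will be based on multivariate regression or support vector machines". On performance: "The ROC will be evaluated with respect to accuracy, area under curve (AUC), sensitivity (true positive rate) and specificity (true negative rate"). Features are kept only if their permutation importance exceeds that of a random variable, and collinearity is examined by partial correlations.

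The same section, and the S2 endpoint definition in section 3 (Secondary hypotheses and secondary endpoints), also specify a chi-square test. In section 3 it relates dichotomised disability change in months 24-36 to dichotomised thalamus volume change over the first 24 months.

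Under Power/Sample Size, Secondary objectives, S2 is sized as a comparison of two proportions: "we assume that 5% of patients in groups 2 and 3 (pooled) show disability progression between month 24 and month 36". Group 1 is taken to have practically no events. The requirement is met "when the size of each of group 1 and the pooled group is 152", at alpha 0.05 and 80% power. No sizing is given for the prediction model.

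The main-phase milestone table (section 3, M-13) refers to more than 350 subjects completing V4 with disability events at about 10% to 15%.

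**The concern.** What limits a model for a binary outcome is the number of events, not the number of patients. Ten or more predictors set against about eight events leave the model free to fit noise, and its apparent discrimination then says little about new patients.

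S2 is worded as a demonstration that thalamus volume change is predictive, and the Synopsis makes the 12-month extension depend on S2 being sufficiently likely to succeed. The protocol does not say whether the chi-square test or the model decides S2. An inflated AUC could therefore be presented as the demonstration. Leaving the choice between regression and a support vector machine open adds a further data-dependent step.

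**Working it through.** **1. The plan's S2 sample size.** Inputs (Power/Sample Size, Secondary objectives): p1 = 0.05, p2 = 0, alpha 0.05 (taken as two-sided; the protocol does not say), power 0.80. With the pooled-variance formula without continuity correction:

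n = [1.960 x sqrt(2 x 0.025 x 0.975) + 0.842 x sqrt(0.05 x 0.95)]² / 0.05² = (0.4327 + 0.1834)² / 0.0025 = about 152 per group.

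This matches the stated 152, so the total is 304. The attrition table also reproduces: 600 x 0.85³ = 368 at month 36.

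**2. Expected events in months 24-36.**

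- At 304 patients: 152 x 0.05 + 152 x 0 = 7.6.
- At 368 patients, with group 1 and the pooled groups about half each (section 4, S1): 184 x 0.05 = 9.2.

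**3. Predictors.** The list has ten features. Therapy is categorical. If it is coded by the five drugs named in the inclusion criteria, it needs four indicators instead of one term, giving 13 parameters. If TVL and BVL each enter once per scan interval, the count is 15. The protocol fixes neither coding.

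**4. Events per parameter.**

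| Expected events | 10 features | 13 parameters | 15 parameters |
|---|---|---|---|
| 7.6 | 0.76 | 0.58 | 0.51 |
| 9.2 | 0.92 | 0.71 | 0.61 |

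**5. Optimism when nothing predicts.** Simulation with 1,500 data sets per scenario: independent standard-normal predictors unrelated to outcome, and an essentially unpenalised logistic fit. The AUC was taken on the fitting data and on new data.

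| Patients | Events | Parameters | Mean AUC, fitting data | 5th-95th percentile | Mean AUC, new data |
|---|---|---|---|---|---|
| 304 | 8 | 10 | 0.79 | 0.68-0.90 | 0.50 |
| 304 | 8 | 13 | 0.83 | 0.73-0.92 | 0.50 |
| 304 | 8 | 15 | 0.85 | 0.75-0.93 | 0.50 |
| 368 | 9 | 10 | 0.78 | 0.68-0.87 | 0.50 |
| 350 | 35 | 10 | 0.65 | 0.60-0.71 | 0.50 |
| 350 | 52 | 10 | 0.63 | 0.58-0.69 | 0.50 |

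In the first scenario 91% of null data sets reached an apparent AUC of at least 0.70. The last two rows take M-13 at face value: 350 x 10% = 35 and 350 x 15% = 52.5 events.

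**6. Precision of an honestly validated AUC.** With 8 events and 296 non-events, the standard error at AUC 0.50 is sqrt(305 / (12 x 8 x 296)) = 0.10, so roughly ±0.20 at 95%. Each event moves sensitivity by 1/8 = 12.5 percentage points.

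**7. Accuracy.** Predicting no progression for everyone gives 1 - 7.6/304 = 97.5%.

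**The case against.** The stronger reading a reader might infer is that S2 as planned would look predictive even if nothing predicts. The documents do not support that, for four reasons.

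- **Data used for the ROC.** The protocol does not say which data the ROC or the feature screening will use. Internal validation and the final model choice are commonly left to a statistical analysis plan, which is not at hand. The inflated AUC is therefore conditional. The mismatch between ten listed features and about eight events does not depend on that silence: validation would expose the optimism but would not make eight events sufficient.
- **The chi-square test.** The S2 endpoint definition and the sample size both rest on a two-group comparison with no multi-predictor fitting. It is untouched by this point.
- **The event count.** M-13 gives a higher level, which may be cumulative from baseline. On that level the optimism is much smaller, though still present. About eight events is the figure on which S2 is sized.
- **Accuracy.** It is to be reported beside sensitivity and specificity, and a classifier that never predicts progression would show sensitivity 0. Accuracy misleads only if read alone.

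Two limits on the size also stand. The simulation used independent predictors and logistic regression. It covered neither a support vector machine nor the permutation screening and partial-correlation check, so 0.79 is not the planned procedure's own figure. Those two checks address relevance and redundancy; neither corrects an AUC for optimism. And 0.50 is the true value only under the null. If all events fell in the pooled groups as assumed, dichotomised TVL alone would have sensitivity 1 and specificity 152/296 = 0.51, an AUC of (1 + 0.51)/2 = about 0.76. A noise model's apparent 0.79 would thus be hard to tell from the signal the plan expects.

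**Conclusion.** The point holds for the prediction model, not for S2 as a whole. By the protocol's own figures, ten listed features (about 13 parameters with therapy coded by drug) face about 8 events, or 9 at the expected retention, and the model has no sizing of its own.

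If performance is read from the fitting data, the AUC with no true predictor averages about 0.79 for ten predictors and 0.83 for 13. Under M-13's event level it averages about 0.63-0.65 for ten. These sizes assume independent predictors, an unpenalised logistic fit and no internal validation. Even a properly validated AUC would be imprecise with so few events.

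**What to change.** 1. State that S2 is decided by the chi-square test for which it is sized.
2. Label the ten-variable regression or support vector machine classifier exploratory.
3. Report its AUC, sensitivity and specificity only after optimism correction, by bootstrap or repeated stratified cross-validation, with feature screening, tuning and the choice of model inside each resample. Give confidence intervals, and do not report accuracy alone.
4. If a model is to support the predictive claim, use a penalised model centred on TVL with very few prespecified covariates. Even three terms would leave 8/3 = 2.7 events per term, so the claim should stay modest.
5. Reconcile the 10-15% of M-13 with the 5% and about 0% of the S2 sample size, saying which period each refers to.

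The cost is wording, modest extra computing and a less favourable reported AUC. No data collection changes.

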## **Secondary Objectives**

- (S1) To demonstrate that worsening of MS-related disability is associated with loss of thalamus volume when loss of whole brain volume is within the normal range.
- (S2) To demonstrate the change of thalamus volume during 24 months is predictive of the change of disability during the following 12 months (months 24-36).

[figure not shown]

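### The S2 prediction model labels a predictor relevant if it beats one random variable, so a useless predictor earns the label about half the time; the S2 chi-square test is not affected

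*Protocol*

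**What the plan says.** Secondary objective S2 (Protocol, section 2) is worded as a demonstration: "To demonstrate the change of thalamus volume during 24 months is predictive of the change of disability during the following 12 months" (months 24 to 36).

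Section 4, under S2, plans two things.

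- **A formal test.** The association of dichotomised disability change with baseline parameters and "TVL between baseline and 24 months will be tested using the chi-square statistic". The secondary endpoints in section 3 also name the chi-square statistic, there for dichotomised TVL.
- **A prediction model.** "The model will be based on multivariate regression or support vector machines". Its performance is described by the ROC curve, accuracy, AUC, sensitivity and specificity. Within each classifier, "permutation importance will be calculated for each feature and for the random variable", and "only parameters whose importance are higher than the random variable's importance, will be considered as relevant in the classifier".

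The random comparator is singular, and the criterion is simply a higher value. The section gives no number of repeats, margin, null distribution, significance level or multiplicity correction for this rule.

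**The concern.** The benchmark is one draw of noise. A feature with no relation to progression is another draw of noise, so which of the two ranks higher is close to a coin toss. This is not overfitting. It cannot be cured by more patients, fewer features or cross-validation, because the threshold itself is a single random value.

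The label matters because TVL is among the candidate features and S2 is about whether TVL is predictive. A report that the classifier found TVL relevant would be read as support for the treatment-target argument in the rationale and in section 5. A useless TVL would earn that statement about half the time. The protocol fixes the rule, so an analysis plan that follows it inherits the error rate. This is therefore not a detail left open for later.

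**Working it through.** **Inputs from the Protocol, section 4**

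- Clinical features ("Clinical scores / characteristics @ BL"): age, sex, disease duration, EDSS, therapy = 5.
- Baseline MRI: "z-scores of thalamus and whole brain volume" (2) and T2 lesion load (1) = 3.
- Longitudinal MRI: TVL and brain volume loss (BVL) = 2. The total is 10.
- S2 effect: "5% of patients in groups 2 and 3 (pooled) show disability progression between month 24 and month 36", against about zero in group 1; type I error 0.05, type II error 0.20; 152 per group, 304 in all.

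**The plan's own figure.** With p1 = 0, p2 = 0.05 and mean 0.025 (two-sided 0.05, power 0.80, no continuity correction):

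n = [1.960·√(2·0.025·0.975) + 0.842·√(0.05·0.95)]² / 0.05² = (0.4327 + 0.1834)² / 0.0025 ≈ 151.9, so 152. The figure reproduces. Expected events are 152 × 0.05 = 7.6.

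**Error rate of the relevance rule.** Under exchangeability:

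- One useless feature against one random variable: P = 1/2.
- k useless features sharing the same comparator: none passes only if the random variable ranks highest of k + 1, so P(at least one passes) = k/(k+1).

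| k useless | P(at least one labelled relevant) |
|---|---|
| 5 | 5/6 = 83% |
| 8 | 8/9 = 89% |
| 10 | 10/11 = 91% |

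The formula 1 − 0.5^k (99.9% for ten) would be wrong, because the comparisons share one comparator.

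**Simulation with useless features.** Exchangeability is only approximate with correlated or binary features, so it was checked.

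| Model and importance | Setting | Useless TVL passes | At least one useless feature passes |
|---|---|---|---|
| Logistic, AUC, in-sample and 5-fold cross-validated | N = 304 or 368; 2.5–15% events; 600 runs per cell | 50–58% | 91–94% |
| Ridge logistic, AUC, in-sample | N = 304, 2.5% events, TVL–BVL r = 0.86; 3,000 runs | 55% | 93% |
| Same, 4-fold cross-validated | 2,000 runs | 48% | 89% |
| Ridge logistic, AUC | N = 3,000, 10% events, r = 0; 150 runs | – | 91% |
| Class-weighted SVM (linear, RBF), AUC, cross-validated | N = 304; 150 runs per cell | 49–59% | 92–94% |
| Class-weighted RBF SVM, accuracy | N = 304, 2.5% events; 150 runs | 49% | 87% |
| Unweighted RBF SVM, accuracy | N = 304, 2.5% or 12.5% events; 150 runs per cell | 0% | 0–2% |

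Where all ten features were useless and importance was AUC-based, about five of ten passed on average. The first row includes cells in which two of the ten features were truly predictive; there the last column counts the other eight. In the last row almost everyone is predicted not to progress, importances tie at zero, and almost nothing is labelled. Monte Carlo standard error at 50% is √(0.25/600) = 2 points for 600 runs and 4 points for 150.

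**Under the S2 effect (0% versus 5%, N = 304).** The protocol gives no TVL–BVL correlation, so it was varied as an assumption (400 runs per cell).

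| r | TVL passes, in-sample | TVL passes, 4-fold cross-validated |
|---|---|---|
| 0 | 94% | 95% |
| 0.5 | 92% | 95% |
| 0.7 | 89% | 90% |
| 0.86 | 82% | 90% |
| 0.9 | 79% | 90% |

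A separate run over r = 0 to 0.9 gave 78–91%, so the overall range is 78–95%.

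**The chi-square test at 152 versus 152 (exact, uncorrected).** With no events in group 1 and x in the other group, the statistic is 304x/(304 − x): 3.03 at x = 3 and 4.05 at x = 4. It rejects from x = 4, and P(Binomial(152, 0.05) ≥ 4) = 94.9%. At 2.5% in both groups it rejects in 4.4%.

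**The case against.** The strongest reply is that the rule does not decide S2. Both the endpoint section and section 4 test the TVL association by chi-square, and the sample size is a two-proportion calculation. This stands. A reader might infer that S2 would be declared in about half of all null worlds. The documents do not support that: the chi-square test rejects in about 4% under the null, and the rule only labels features inside the classifier.

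A reader might also infer that the rule hardly separates an effect from no effect. That does not hold either. TVL passes in 78–95% of runs under the assumed effect, against about 50% under none, and the low end of that range needs a high assumed TVL–BVL correlation and in-sample importance.

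Nor can 91% be quoted without conditions. It requires all ten features to be useless, whereas the covariate table in section 3 itself calls baseline EDSS a predictor of progression. It also requires AUC-type importance or similar. The plan leaves the classifier and metric open, and an unweighted RBF SVM scored by accuracy labels almost nothing. That is a different failure of the rule and does not rescue it.

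The collinearity analysis in section 4 deals with redundancy between features and does not control false labels. It is also fair that S2 belongs to an extension that runs only if sample-size conditions are met. That lowers the stakes but leaves the rule wrong.

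**Conclusion.** The concern holds for the label. As fixed in the protocol, and with AUC-type importance, the rule calls a useless TVL relevant about half the time. At least one of k useless features passes with probability about k/(k+1), which is 83% for five and 91% for ten, whatever the sample size and with or without cross-validation. The 50% figure for TVL does not depend on how many other features are useless. Correlated or binary features shift the rates by a few points.

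The type I error of the S2 chi-square test is unaffected. What is at risk is any statement that TVL, or another listed parameter, was found relevant by the classifier. The result rests on approximate exchangeability of a useless feature with the random variable and on an importance measure that does not collapse to ties.

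**What to change.** **Preferred.** Delete the single-random-variable rule. Report the permutation-importance ranking as descriptive only, and say that the S2 conclusion on TVL rests on the chi-square test already planned. This costs one sentence and changes no procedure or sample size.

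**If a relevance label is kept.** Require a feature's importance to exceed a threshold from its own null distribution, obtained by refitting with permuted outcome labels, and correct for the number of features. With ten features a Bonferroni level is 0.05/10 = 0.005. The smallest attainable p-value with B permutations is 1/(B + 1), so B must be at least 199; 99 permutations stop at 0.01, while 1,000 give about 0.001.

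Two shortcuts need care. Using the average importance of the random variable as the threshold does not help: in simulation a useless TVL still passed in 39–54% of runs and at least one useless feature in 97–100%. Requiring a feature to beat the maximum of m random variables gives 1/(m+1) per feature and 10/(10+m) for any of ten. So m = 19 gives 5% and 34%, and m = 199 gives 0.5% and 4.8%.

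**Downside.** Fewer features will be labelled relevant, and a permutation threshold has low power with about 7.6 expected events. In simulation (99 permutations, 150 runs, no correction for ten features) it passed TVL in about 25% of runs under 0% versus 5%, and in 4% under the null. The corrected version was not simulated and presumably has lower power. That favours the descriptive option.

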#### Secondary data analysis

The investigators have access to a large brain MRI database of MS patients sampled over the past 3 to 4 years from multiple centers across Germany. We will select MS patients from the brain MRI database whose data match best the requirements of the prospective observational study. Since EDSS scores are sparsely available, missing clinical data will be retrospectively collected by the investigators from the associated neurology centers. Then, we will compare three alternative methods to measure TVL and associations with change in EDSS: The Jacobian method as described in (Opfer et al. 2020) uses a longitudinal registration technique which is based on a pairwise inverse-consistent highly elastic diffeomorphic alignment of baseline (BL) and the follow-up (FU) scans to the halfway image space of the subject. The approach incorporates rigid registration into a halfway image space (an image space between BL and FU image) and correction for intensity inhomogeneities. The output Jacobian is the composition of two Jacobians: the Jacobian of the transformation field from the halfway space image to the FU scan and the negative Jacobian from the halfway image to the BL scan. Each voxel of the Jacobian therefore describes the percentage volumetric change between BL and FU image for that particular voxel location. To estimate the volumetric change of certain subregions of the brain the signal of the Jacobian needs to be integrated over a region of interest. The above approach is based on an elastic registration of the whole brain image. As an alternative technique the above approach will be deployed for a region around the structure of interest (ROI) (the thalamus for example). The two images will be registered into a halfway space. In both images a bounding box around the ROI will be extracted from the whole image. The above-described steps will be performed using the bounding boxes instead of the whole brain image. The third approach uses a segmentation of the ROI in the baseline image. The highly elastic diffeomorphic registration will be used to compute a displacement field of the boundary of the ROI. From the displacement fields at the boundary a volume change can be determined. The three methods will be compared with respect to stability and sensitivity using the cohorts and methods described in Opfer et al. (2020). The most suitable method will qualify for application to the primary data. Important conclusions regarding the statistical design can be drawn from the results.
